5.0 Patient Eligibility

Inclusion Criteria:

Patients will be eligible for inclusion in the study if they meet all of the following criteria:

1. Patients age > 18 years at the time of signing informed consent. Understand and voluntarily sign an informed consent.

2. Patients with CLL or SLL with active disease.
3. Prior treatment with purine analog based chemotherapy or chemoimmunotherapy.
4. Platelet count $\geq 30,000 \text{ mm}^3$
5. ECOG/WHO performance status of 0-2
6. Adequate renal function indicated by creatinine clearance $> 30 \text{ ml/min}$ (calculated by 24 hours urine collection) or a GFR $> 30 \text{ ml/min}$ estimated using the Cockcroft-Gault equation. Adequate hepatic function indicated as total bilirubin less or equal to 2 mg/dl and ALT less or equal to two times the upper limit of normal.
7. Disease free of prior malignancies for 3 years with exception of currently treated basal cell, squamous cell carcinoma of the skin, or carcinoma "in situ" of the cervix or breast. Patients with malignancies with indolent behavior such as prostate cancer treated with radiation or surgery can be enrolled in the study as long as they have a reasonable expectation to have been cured with the treatment modality received.
8. Females of childbearing potential (FCBP)[†] must have a negative serum or urine pregnancy test with a sensitivity of at least 50 mIU/mL within 10 – 14 days prior to starting lenalidomide and again within 24 hours prior to prescribing lenalidomide (prescriptions must be filled within 7 days) and prior to first administration of ofatumumab and must either commit to continued abstinence from heterosexual intercourse or begin TWO acceptable methods of birth control, one highly effective method and one additional effective method AT THE SAME TIME, at least 28 days before she starts taking lenalidomide and continue it for 6 months after therapy has been completed. FCBP must also agree to ongoing pregnancy testing. Men must agree to use a latex condom during sexual contact with a FCBP even if they have had a successful vasectomy. All study participants must be registered into the mandatory RevAssist® program, and be willing and able to comply with the requirements of RevAssist®. See Appendix: Risks of Fetal Exposure, Pregnancy Testing Guidelines and Acceptable Birth Control Methods.

Exclusion Criteria:

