[†] A female of childbearing potential is a sexually mature woman who: 1) has not undergone a hysterectomy or bilateral oophorectomy; or 2) has not been naturally postmenopausal for at least 24 consecutive months (i.e., has had menses at any time in the preceding 24 consecutive months).

1. Known sensitivity to lenalidomide, other thalidomide derivatives or ofatumumab.
2. Documented prolymphocytic leukemia (prolymphocytes more than 55% in the blood).
3. Known positivity for HIV or active hepatitis B or C.

Known positivity for HIV or active hepatitis B or C. Positive serology for hepatitis B (HB) defined as a positive test for HBsAg. In addition, if negative for HBsAg but HBcAb positive regardless of HbsAb status, a HB DNA test will be performed and if positive the subject will be excluded.

4. Pregnant or breast feeding females. Women of childbearing potential must have a negative pregnancy test at screening. Male subjects unable or unwilling to use adequate contraception methods from study start to one year after the last dose of protocol therapy.
5. Chronic or current infectious disease requiring systemic antibiotics, antifungal, or antiviral treatment such as, but not limited to, chronic renal infection, chronic chest infection with bronchiectasis and tuberculosis. History of tuberculosis treated within the last five years or recent exposure to tuberculosis.
6. Any serious medical condition, laboratory abnormality, or psychiatric illness that places the subject at unacceptable risk if he/she were to participate in the study.
7. Patients with a recent history of deep vein thrombosis (DVT) or pulmonary embolus (PE), in the six months prior to enrollment are not eligible for this study.
8. Treatment with any known non-marketed drug substance or experimental therapy within 5 terminal half lives or 4 weeks prior to enrollment, whichever is longer, or currently participating in any other interventional clinical study
9. Prior treatment with other monoclonal antibodies within 4 weeks prior to enrollment.
10. Subjects meeting any of the following criteria must not be enrolled on study: Positive serology for Hepatitis B (HB) defined as a positive test for HBsAg. In addition, if negative for HBsAg but HBcAb positive (regardless of HBsAb status), a HB DNA test will be performed and if positive, the subject will be excluded.

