The MDACC "Internal SAE Report Form for Prompt Reporting" will be used for reporting to ORERM.

Serious adverse events will be captured from the time the patient signs consent until 30 days after the last dose of lenalidomide and for a minimum of 5 half lives (6 months) after the last dose of ofatumumab. If a subject does start other therapy, then SAEs will no longer be required to be reported.

Serious adverse events must be followed until clinical recovery is complete and laboratory tests have returned to baseline, progression of the event has stabilized, or there has been acceptable resolution of the event.

Additionally, any serious adverse events that occur after the 30 day time period that are related to the study treatment must be reported to ORERM. This may include the development of a secondary malignancy.

Reporting to FDA:

Serious adverse events will be forwarded to FDA by the IND Sponsor (Safety Project Manager ORERM) according to 21 CFR 312.32.

It is the responsibility of the PI and the research team to ensure serious adverse events are reported according to the Code of Federal Regulations, Good Clinical Practices, the protocol guidelines, the sponsor's guidelines, and Institutional Review Board policy.

NOTE: Instructions concerning procedures and reporting for pregnancies below.

Pregnancies

Pregnancy of a female subject or the female partner of a male subject occurring while the subject is on lenalidomide and ofatumumab or within 4 weeks after the

subject's last dose of lenalidomide or ofatumumab are considered expedited reportable events. If the subject is on lenalidomide, it is to be discontinued immediately and the subject is to be instructed to return any unused portion of lenalidomide to the Investigator. The pregnancy must be reported by the investigator to MDACC IRB and ORERM AND to Celgene Corporation Worldwide Drug Safety Surveillance (WWDSS) and to GSK within 24 hours of the Investigator's knowledge of the pregnancy by phone and facsimile using the SAE Form.

The Investigator will follow the subject until completion of the pregnancy, and must notify Celgene Corporation Worldwide Drug Safety Surveillance (WWDSS) of the outcome as specified below. The Investigator will provide this information as a follow-up to the initial SAE.

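### A pregnancy is itself reportable only until 4 weeks after the last dose, while SAEs are captured for 6 months after ofatumumab, so some pregnancies in that period go unreported and unfollowed.

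*Combined protocol and SAP*

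**What the plan says.** Under Pregnancies, Section 9.0 sets the reporting period with the words "while the subject is on lenalidomide and ofatumumab or within 4 weeks after the". The 4 weeks are counted from the final dose of either drug. Such pregnancies need expedited reporting: they go to the IRB, the sponsor's office and both companies within 24 hours, and the investigator then follows the pregnancy to its end.

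Earlier in Section 9.0, SAE capture is set drug by drug. For lenalidomide it starts at consent and stops 30 days after the final dose. For ofatumumab it lasts "for a minimum of 5 half lives (6 months) after the last dose of ofatumumab". It ends if the subject starts other therapy. SAEs after the 30-day period are still reportable if they are related to study treatment.

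Other post-treatment periods differ:
- Section 5.0, inclusion 8: women use contraception from "at least 28 days before she starts taking lenalidomide and continue it for 6 months after therapy has been completed".
- Section 5.0, exclusion 4: men use "adequate contraception methods from study start to one year after the last dose of protocol therapy".
- Section 6.0: the last scheduled pregnancy test is on Day 28 after the last lenalidomide dose.
- Section 7.0: contraception continues for at least 28 days after leaving the study.

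**The concern.** The SAE rule treats the two drugs separately and justifies the longer ofatumumab period by half-life. The pregnancy rule applies one period to both drugs, and that period is close to the 30 days used for lenalidomide SAEs. Six months is also the ofatumumab horizon elsewhere. Section 7.0 places liver function tests 6 months after the last dose, and in the at-risk subgroup it continues hepatitis B DNA monitoring up to 6 months.

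A contraceptive failure in, say, the third month after both drugs stop is the kind of event the 6-month requirement for women is meant to prevent. As written, the resulting pregnancy would not be a reportable event, and the duty to follow it to completion would not begin. The trial would then learn of some bad outcomes without knowing how many pregnancies they came from.

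**Working it through.** No sample size or error rate is involved, so the check compares the periods and uses date arithmetic.

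**Inputs.** The pregnancy window is 4 weeks = 28 days (Section 9.0). The ofatumumab SAE window is 6 months, taken as 183 days; counting 6 months as 168 to 184 days shifts the results slightly. Under Section 4.0, lenalidomide is daily for 24 cycles of 28 days and may continue longer. Ofatumumab is given every two months in months 7 to 24.

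**Reading of the rule.** A pregnancy within 4 weeks of the last dose of either drug qualifies, so the window closes 28 days after whichever drug stops last. I take being on treatment to mean being on either drug.

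**Formula.** If lenalidomide continues x days after the last ofatumumab dose, the part of the 6 months left uncovered is 183 − (x + 28) = 155 − x days, and never less than zero.

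| Case | x (days) | Window closes, days after ofatumumab | Uncovered days |
|---|---|---|---|
| Both drugs stop together | 0 | 28 | 183 − 28 = 155 |
| Lenalidomide runs 4 weeks longer | 28 | 56 | 183 − 56 = 127 |
| Lenalidomide runs about 5 months longer | 152 | 180 | 183 − 180 = 3 |

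The second case assumes that the final ofatumumab dose falls on day 1 of month 24, that a month equals a cycle, and that lenalidomide stops at the end of cycle 24. The documents do not fix this timing. In the first case the uncovered share is 155/183 = 85%; in the second it is 127/183 = 69%. With 6 months counted as 168 or 184 days, the first case gives 140 or 156 days.

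**Residual drug, on the protocol's own equation.** Five half-lives in 6 months imply a half-life of 183/5 = 36.6 days. At day 28 that is 28/36.6 = 0.77 half-lives, so 2^(−0.77) or about 59% would remain, against 2^(−5) = 3.1% at five half-lives. The documents give no serum half-life; the 180 minutes in Section 2.0 concerns dissociation from the cell surface. With assumed half-lives of 14, 21 or 28 days, 25%, 40% or 50% would remain at day 28, and five half-lives would end 42, 77 or 112 days after it.

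**Do other rules in Section 9.0 close the gap?**
- *Suspected fetal exposure* is reportable with no time limit, but the rule names lenalidomide only.
- *SAE capture* reaches a pregnancy only if its outcome is an SAE, such as a congenital anomaly. Pregnancy itself is not on the SAE list. A pregnancy that begins in month 3 and goes to term ends after the 6-month window, when only related SAEs remain reportable.
- *Neonatal deaths* within 30 days of birth are reportable whatever their cause.
- *Start of other therapy* ends SAE reporting.
- *Scheduled testing* ends at Day 28 after lenalidomide, so it would not reveal these pregnancies.

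These rules narrow the gap but leave part of it open.

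**The case against.** The strongest reply is that 4 weeks is not out of line with the protocol. It agrees with the last pregnancy test in Section 6.0 and the 28-day contraception period in Section 7.0, and nearly agrees with the 30-day SAE period for lenalidomide. That stands. A reader might infer that the pregnancy window is shorter than every post-treatment period in the protocol, and the documents do not support this. The protocol uses 28 days, 6 months and one year in different places. The specific mismatch is with the ofatumumab SAE period and the Section 5.0 contraception periods.

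A reader might also infer that a pregnancy in the gap produces no report at all. That is too strong, because several adverse outcomes still have a reporting route.

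It would be equally wrong to treat 155 days as typical. It is a maximum, and it shrinks day for day as lenalidomide continues after ofatumumab.

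Finally, one might count about 11 of the 12 contraception months for men as uncovered exposure. Section 5.0 states that year as an eligibility condition for protocol therapy as a whole and says nothing about drug persistence. A 6-month reporting window would not cover it either.

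Two limits remain. That ofatumumab exposure lasts 6 months is inferred from an SAE rule, though the stated half-life basis makes the inference reasonable. The appendices on fetal exposure and adverse event reporting are cited but were not in the text available to me, so they may add rules. What survives is that nothing in the text reviewed makes a pregnancy itself reportable after the 4-week window closes, unless fetal exposure to lenalidomide is suspected.

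**Conclusion.** The point holds in limited form. For ofatumumab, the pregnancy-reporting window ends before the SAE window in the same section. The uncovered period ranges from about 155 days to almost none, depending on how long lenalidomide outlasts ofatumumab. The pregnancies likely to be missed are uncomplicated ones, those whose outcomes arise after 6 months and are not judged related, and those that occur after other therapy begins. For lenalidomide alone there is little to correct.

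The conclusion rests on the later-drug reading of the window, on 6 months being about 183 days, and on the cited appendices adding no further reporting rule. With at most 36 patients, few pregnancies are to be expected. This is a gap in safety reporting that should be closed; it does not touch the response endpoint, the sample size or the stopping rules.

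**What to change.** In the Pregnancies part of Section 9.0, give ofatumumab the same post-dose reporting window that the section already uses for ofatumumab SAEs. Keep the 24-hour route and the follow-up to completion as they are.

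Separately, the sponsor should reconcile the post-treatment contraception and testing periods: 6 months and one year in Section 5.0, Day 28 in Section 6.0, and 28 days in Section 7.0. Which of these is right is for the sponsor to decide.

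The reporting change is one sentence. The reconciliation touches three sections and any patient material that repeats them. The running cost is at most a few extra reports.

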10.0 Statistical Design

This is a single-arm, phase II study of combination of lenalidomide and ofatumumab. The study population consists of patients with previously treated CLL/SLL and patients will have to have received at least one purine analog-based regimen. The primary outcome is overall response. A Simon's two-stage minmax design will be used for this study. A sample size of 36 is chosen to differentiate between a good response rate of 40% and a poor response rate of 20% with 90% power at a significance level of 0.1. In particular, 19 patients will be enrolled at the first stage. If there are 3 or fewer responses in the first 19 patients, accrual will be suspended until we have 4 responders among the first 19 patients. The trial will be terminated if all 19 patients have been evaluated for 6 cycles and there are 3 or fewer responses; otherwise another 17 patients will be treated for a total of 36 patients. If there are 10 or fewer responses among 36 patients, the treatment will be concluded ineffective. The probability of early termination due to futility is 0.46. Overall response includes complete remission (CR) and partial remission (PR). Patients are considered non-responders if there is progression of disease. CR, PR and SD allow continuation of treatment.

The probability of toxicity (grade 3 and 4 non-hematological) will be monitored based on the Bayesian model (beta-binomial) by assuming a priori probability of toxicity following Beta (1,1). The trial will be terminated if $\text{Prob}(\text{toxicity} > 0.33 \mid \text{data}) > .85$. Following this rule, the trial will be terminated if $[\# \text{ toxicities}]/[\# \text{ patients evaluated}] \geq 3/5, 5/10, 7/15, 9/20, 11/25, 13/30, \text{ and } 15/35$. A simulation study was performed to show the operating characteristics for the stopping rule based on 10,000 repetitions. The results are summarized in the

following table. For example, the trial will be terminated early 90.8% of times if the true toxicity rate is 50%.

True Prob(tox)	Pr(stop)	Median #Pts (25%, 75%)
0.10	0.011	36 (36, 36)
0.20	0.084	36 (36, 36)
0.30	0.305	36 (15, 36)
0.40	0.646	15 (5, 36)
0.50	0.908	10 (5, 15)
0.60	0.991	5 (5, 10)

The first time point to evaluate efficacy and toxicity will be at completion of cycle 6 of treatment. Toxicity will be monitored closely during the entire treatment, but toxicities occurring after cycle 6 will not be applied to the stopping boundaries. The descriptive statistical analysis can be used to explore the data, including histograms or box-plots, proportions, mean, standard deviations. The Fisher's exact test will be used for the univariate analysis on categorical variables (response variable with Yes versus No, for example). The t-test or Wilcoxon test will be used for continuous variables (Age and WBC, for example). Descriptive statistical analysis will also be used to report correlative studies and the quality of life questionnaire.

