2.0 Background

CLL is the most common form of adult leukemia in the United States. It has been estimated that there are approximately 150,000 individuals living with CLL in the United States. The use of combination of chemoimmunotherapy as initial therapy is associated with a high response rates. Unfortunately, once disease relapse has been observed second line treatment is less effective and responses obtained tend to be shorter(1). A treatment for second line consists in the use of the monoclonal antibody (mAb) alemtuzumab. Alemtuzumab is able to induce a response in up to 30% of the patients, but is associated with significant immunosuppression. Also, it lacks activity in patients that have developed bulk lymphadenopathies (larger than 5 centimeters)(2). Combination of purine-analogue based regimens have limited activity: the combination of fludarabine, cyclophosphamide, rituximab, alemtuzumab (CFAR) is associated with an overall response rate of 65% in patients that have received prior therapy and once patients are fludarabine refractory their median survival is less than twelve months based on our published experience (3,4).

Lenalidomide is a thalidomide derivative with immunomodulatory and anti-angiogenic properties. Lenalidomide has been studied in patients with previously treated CLL as a single-agent and has shown encouraging activity with an overall response rate of 30-50% (5,6). The mechanism of action of lenalidomide in CLL is not completely known at this point: there is indication that its activity could be mediated through the stimulation of the immune system. An increased number of circulating T-cells has been observed in patients with CLL treated with this agent. Lenalidomide has also the ability to affect the interaction between the leukemic cells and the bone marrow stromal cells and T-cells (supported by pre-clinical data) and is able to suppress TNF-alpha and alter the cytokines milieu that is potentially important for CLL proliferation (7,8).

Ofatumumab is a novel anti-CD20 mAb, and has potential advantages over rituximab in the specific setting of CLL. Ofatumumab is a fully human monoclonal antibody (IgG1) produced via a transgenic mouse technology and binds specifically to a unique epitope on the human CD20 molecule expressed on B-

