cells. Ofatumumab has shown clinical activity in a phase II study of patients with refractory CLL, the overall response rate was 58% in patients refractory to fludarabine and alemtuzumab and 47% in patients with bulky lympho-nodes and refractory to fludarabine (9, 10). The toxicity profile was favorable with mainly infusion-related reactions.

On human tissue sections ofatumumab demonstrated tissue reactivity that is consistent with its target antigen specificity. Following the binding of ofatumumab to tumor B-cells clustering of CD20 into lipid rafts, as seen with rituximab, was observed. Strong differences in antibody cell-surface off-rates were detected between ofatumumab and rituximab. Ofatumumab dissociated much more slowly from surface CD20 than rituximab, corresponding to a half life of 180 minutes for ofatumumab and 90 minutes for rituximab. In this respect, both efficient clustering into rafts and a lower off-rate value for ofatumumab are important characteristics for an effective activation of the complement and may explain the superiority of ofatumumab over rituximab in CDC of B-cells. Ofatumumab-CD20 was able to induce complement-mediated lysis of freshly isolated human B-CLL tumor cells, and rituximab-resistant cells lines expressing low levels of CD20 and high levels of CD55/CD59, which is known to diminish the lytic effect of complement. Ofatumumab -CD20- and rituximab-mediated Antibody Dependent Cell-mediated Cytotoxicity (ADCC) were equivalent. In an in vivo study employing a SCID mouse tumor model, HuMax-CD20-treated animals showed a dose-dependent prolongation of survival that was superior to rituximab. A pilot pharmacokinetic study in cynomolgus monkeys demonstrated that depletion of CD20 expressing B lymphocytes occurred rapidly after antibody administration. Depletion of B cells with ofatumumab lasted four times longer than depletion observed after administration of a similar dose of rituximab (11,12)

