The rationale for combining lenalidomide and ofatumumab is to potentiate the clinical efficacy of these agents without increasing their toxicity. This is based on different mechanisms of action and non-overlapping toxicity profile. The toxicity of ofatumumab consists mainly in infusion reactions and lenalidomide toxicity consisting mainly of early myelosuppression, fatigue, skin rash, diarrhea, and tumor flare. There is also the possibility that the combination will ameliorate the tumor flare reaction seen with lenalidomide because of the rapid reduction in tumor burden seen with anti-CD20 mAb therapy. Because of the debulking properties of ofatumumab, lenalidomide will be started on day 9, after two doses of ofatumumab have been administered.

Current experience with the combination of lenalidomide and the anti-CD20 mAb rituximab (MDACC study 2007-0208) shows favorable activity with 7 of the first 12 patients responding and 8 non-hematological grade >3 adverse events during the 39 treatment cycles administered (data on file).

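### Is the 20% poor response rate too low, given the rates that the protocol reports for each drug alone?

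*Combined protocol and SAP*

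**What the plan says.** Section 10.0 (Statistical Design) sets a single-arm Simon two-stage minimax design with overall response as the primary outcome, 90% power and a significance level of 0.1. The rates are given as: "A sample size of 36 is chosen to differentiate between a good response rate of 40% and a poor response rate of 20" percent. The interim rule begins: "If there are 3 or fewer responses in the first 19 patients, accrual will be suspended until we have 4 responders among the first 19". Termination follows if all 19 have been evaluated for 6 cycles with no more than 3 responses. The final rule is: "If there are 10 or fewer responses among 36 patients, the treatment will be concluded ineffective". The stated probability of early termination is 0.46.

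Section 1.0 (Objectives) makes a response rate of at least 40% the target for the combination.

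Section 2.0 (Background) gives these response rates:
- Lenalidomide alone in previously treated CLL: "has shown encouraging activity with an overall response rate of 30-50" percent.
- Ofatumumab alone: "the overall response rate was 58% in patients refractory to fludarabine and alemtuzumab and 47% in patients with bulky" (the second group had bulky nodes and fludarabine-refractory disease).
- Lenalidomide plus rituximab in another study: "shows favorable activity with 7 of the first 12 patients responding".
- A different second-line option: "Alemtuzumab is able to induce a response in up to 30% of the patients".

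Section 5.0 (Patient Eligibility) asks for "Prior treatment with purine analog based chemotherapy or chemoimmunotherapy" and does not require refractory disease.

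**The concern.** A poor rate should mark activity that is not worth pursuing. Section 10.0 gives no source for 20%, and nothing in Section 2.0 is that low for either drug. The only cited figure that could cover it is alemtuzumab's, and alemtuzumab is not in the regimen. The ofatumumab rates come from refractory patients, whereas this trial also admits patients who are not refractory, so a harder population is not an obvious explanation.

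Section 2.0 says the purpose of combining the drugs is to strengthen their effect. If 20% is too easy to beat, the rule would pass many regimens that add nothing to their components. The futility stop would also seldom act within the range the protocol itself cites, so nearly all 36 patients would be enrolled on a two-drug regimen of limited value.

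**Working it through.** **Inputs.** From Section 10.0: stage 1 size 19, stop at 3 or fewer; total 36, ineffective at 10 or fewer; rates 20% and 40%; level 0.1; power 90%; early termination 0.46. From Section 2.0: 30-50% (lenalidomide), 47% and 58% (ofatumumab), 7 of 12 (lenalidomide plus rituximab). From Section 1.0: target 40%.

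**Formulas.** With true rate p and X1 ~ Bin(19, p):
- P(stop at stage 1) = P(X1 ≤ 3).
- P(pass) = sum over x ≥ 4 of P(X1 = x) × P(Bin(17, p) ≥ 11 − x).
- Expected N = 19 + 17 × [1 − P(stop)].

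**The plan's own figures.** At p = 0.20, P(stop) = 0.0144 + 0.0685 + 0.1540 + 0.2182 = 0.455, against the stated 0.46. The exact level is 0.086 and the power at 40% is 0.902. An exhaustive minimax search at level 0.1 and power 0.90 returns exactly 3/19, 10/36. The design is right for its inputs.

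**The same rule at the Section 2.0 rates.** At p = 0.30, P(stop) = 0.0011 + 0.0093 + 0.0358 + 0.0869 = 0.133, and expected N = 19 + 17 × 0.867 = 33.7. The alternative keeps the same stage sizes but tests 30% versus 50%: stop at 5 or fewer of 19, ineffective at 14 or fewer of 36.

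| True rate | Current: stop / pass | Alternative: stop / pass |
|---|---|---|
| 20% | 0.455 / 0.086 | 0.837 / 0.002 |
| 30% | 0.133 / 0.523 | 0.474 / 0.089 |
| 40% | 0.023 / 0.902 | 0.163 / 0.471 |
| 47% | 0.005 / 0.983 | 0.055 / 0.780 |
| 50% | 0.002 / 0.993 | 0.032 / 0.870 |
| 58% | <0.001 / >0.999 | 0.005 / 0.981 |

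At 30% the alternative lowers expected N from 33.7 to 27.9. Its power at 50% is 0.870, below the plan's 90%. Restoring 90% power takes 39 patients (7/28, 15/39: level 0.094, power 0.900) or 42 (5/19, 16/42: level 0.091, power 0.904). At a true 40% these two designs pass with probability 0.508 and 0.514.

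**What 7 of 12 can show.** P(7 or more of 12) is 0.0039 at 20% and 0.0386 at 30%. The exact 95% interval is 27.7% to 84.8%. The one-sided calculation that counts against 20% also counts against 30%, so it does not favour 30% as the replacement. These patients also received a different antibody, and the protocol does not describe their population. This is indirect evidence only.

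**The case for a change.** The strongest case for a change is that 20% is unsupported and the weakness shows in the plan's own terms. At the bottom of the lenalidomide range, the trial passes about half the time and stops early in only 13% of cases. The smallest passing result is 11/36 = 30.6% (exact 95% interval 16% to 48%), which is below the Section 1.0 target. With no added patients, the 5/19, 14/36 rule would cut the false pass at 30% from 52% to 9%.

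The figures stand, and so does the observation that no reason is given. Three things keep them from requiring a change.

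- **The redesign does not cure the stated harm.** A regimen that only matches ofatumumab alone would still pass with probability 0.78 at 47% and 0.98 at 58%. The large gain appears at 30%, the lowest end of one drug's range. A single-arm trial of this size cannot isolate the contribution of each drug under either rule.
- **The price falls on the sponsor's target.** At 40%, the rate that Section 1.0 says is worth finding, the pass probability drops to 0.47, or about 0.51 with 39 or 42 patients. Adopting the alternative means rewriting the primary objective.
- **Comparability is unknown.** Section 2.0 gives no sample sizes for the single-agent rates. Section 5.0 sets no limit on prior lines, does not exclude refractory disease and admits ECOG 2. A poor rate may also be tied to available second-line therapy, and the alemtuzumab figure of up to 30% is compatible with 20%.

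Timing also counts against a change. The study is open label at one center, and the suspension rule needs a running count of responders. Moving the cut-offs once responses are known would be data-driven.

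**Conclusion.** No change is needed. The choice of 20% versus 40% is a permissible screening trade-off. It protects a 40% regimen with power 0.90 and accepts a 0.52 chance of passing a regimen whose true rate is 30%. The stated design figures reproduce, and Section 10.0 says only when the treatment will be concluded ineffective. It does not present a pass as evidence of gain over either drug.

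The missing reason for 20% is a gap in justification and does not affect the analysis. A competent report will give the response rate with an exact confidence interval, read 11 or more of 36 as evidence of a rate above 20%, and leave comparison with single-agent figures to discussion. None of that needs an amendment.

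This conclusion rests on three assumptions: 40% remains the sponsor's target; the pass probabilities ignore the separate toxicity stop, which could end the trial sooner; and 30% as an alternative poor rate is a reviewer's assumption, taken as the lowest component figure in Section 2.0. A sponsor who wanted the trial to screen against single-agent activity could weigh the stricter rule, but the documents do not set that aim for the primary analysis.
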